#### **5.4 Cycle 1 day 8, Subsequent cycles day 1 and day 8**

- See section 6 for Criteria for Treatment Continuation and dosing delays/modifications
- Review concomitant medications
- Perform physical examination with vital signs (temperature, heart rate, blood pressure, oxygen saturation, respiratory rate, and weight) and ECOG performance status
- Laboratory testing
  - CBC with differential
  - Chemistries: sodium, potassium, chloride, bicarbonate, BUN, creatinine, glucose, calcium, phosphorus, magnesium, total bilirubin, alkaline phosphatase, AST, ALT, total protein, albumin
- ECG for QTc on day 1 of each cycle for cycles 2 and 3. See section 6.3. ECG monitoring on day 1 should be continued for patients with bradyarrhythmias, patients on drugs known to prolong the QT, and patients with electrolyte abnormalities. If there is no QT prolongation for cycles 2 and 3, ECG monitoring on day 1 may be discontinued.
- Administer Eribulin if treatment criteria are met
- It is recommended to correct hypokalemia and hypomagnesemia to grade 1 or better prior to treatment

- HOLD Eribulin administration if:
  - ANC <1000/mm^3
  - Platelets < 75,000/mm^3
  - CTCAE Grade 3 or 4 AE attributable to Eribulin with the specific exclusion of Grade 3 or 4 lymphopenia or Grade 3 hypophosphatemia, hypokalemia, hypocalcemia or hypomagnesemia responsive to oral supplementation

## 5.5 Eribulin Administration

Eribulin will be administered of 1.4 mg/m^2 as an IV infusion over 2-5 minutes on Days 1 and 8 of every 21-day cycle.

Before dose administration, the amount of Eribulin mesylate needed for each subject must be calculated in the following manner:

1. Scheduled dose (mg/m^2) × body surface area (m^2) = Dose (mg)
2. Dose (mg) × 2 = the number of mL of Eribulin mesylate to withdraw from vials for administration.

Body surface area (BSA) will be calculated using the Dubois formula on day 1 of each cycle or per institution standard of care.

Height and body weight will be recorded during the Screening Period. Thereafter, body weight will be recorded on Day 1 of each treatment cycle to recalculate BSA (in the event that weight has changed by 5% or more).

## 5.6 General Concomitant Medication and Supportive Care Guidelines

Any medications, with the exceptions noted below, which are considered necessary for the patient's welfare, and which are not known to interact with the study medication, may be given at the discretion of the Investigator, providing the medications, the doses, dates and reasons for administration are recorded in the eCRF.

In addition, any unplanned diagnostic, therapeutic or surgical procedure performed during the study period must be recorded in the eCRF.

All medications (prescriptions or over-the-counter medications) continued at the start of the trial or started during the study or until 30 days from the end of the last protocol treatment and different from the study medication must be documented.

Contraception:

Patients of child bearing potential and their partners, who are sexually active, must agree to the use of two highly effective forms of contraception throughout their participation in the study and for 4 months after last dose of study drug(s).

- Condom with spermicide and one of the following:
- Oral contraceptive or hormonal therapy (e.g. hormone implants)

- Placement of an intra-uterine device

Acceptable non-hormonal birth control methods include:

- Total sexual abstinence. Abstinence must be for the total duration of the study and the drug washout period.
- Vasectomised sexual partner plus male condom. With participant assurance that partner received post-vasectomy confirmation of azoospermia
- Tubal occlusion plus male condom with spermicide
- Intrauterine Device (IUD) plus male condom+spermicide. Provided coils are copper-banded

Acceptable hormonal methods:

- Etonogestrel implants (eg, Implanon, Norplan)+male condom with spermicide
- Normal and low dose combined oral pills+male condom with spermicide
- Norelgestromin/ethinyl estradiol (EE) transdermal system+male condom with spermicide
- Intravaginal device+male condom with spermicide (eg, EE and etonogestrel)
- Cerazette (desogestrel)+male condom with spermicide. Cerazette is currently the only highly efficacious progesterone based pill.

Growth factor is permitted according to institution and national guidelines.

No drug-drug interactions are expected with cytochrome P-450 (CYP) 3A4 inhibitors and P-glycoprotein (P-gp) inhibitors. The effect of ketoconazole, a strong inhibitor of CYP3A4 and a P-gp inhibitor, on the PK of eribulin was studied in an open-label, two-treatment, two-sequence, two-way crossover trial in 12 subjects with advanced solid tumors. The mean dose-normalized AUC values were similar when eribulin was administered with or without ketoconazole (ratio of the mean AUC: 0.97; 90% CI, 0.83 - 1.12). Population PK analysis showed no effect of CYP3A4 inducers on eribulin exposure. Eribulin does not inhibit CYP1A2, CYP2C9, CYP2C19, CYP2D6, CYP2E1 or CYP3A4 enzymes or induce CYP1A2, CYP2C9, CYP2C19 or CYP3A4 enzymes at relevant clinical concentrations. Eribulin is not expected to alter the plasma concentrations of drugs that are substrates of these enzymes.

Palliative Radiation:

Patients are permitted to receive palliative radiation at any point provided the radiated lesion is not a RECIST 1.1 target. Eribulin should be held during radiation.

## **5.7 Criteria for Taking a Participant Off Protocol Therapy**

Duration of therapy will depend on individual response, evidence of disease progression and tolerance. In the absence of treatment delays due to adverse event(s), treatment may continue until one of the following criteria applies:

- Disease progression
- Intercurrent illness that prevents further administration of treatment
- Unacceptable adverse event(s)

- Participant demonstrates an inability or unwillingness to comply with the medication regimen and/or documentation requirements
- Participant decides to withdraw from the protocol therapy
- General or specific changes in the participant's condition render the participant unacceptable for further treatment in the judgment of the treating investigator

Participants will be removed from the protocol therapy when any of these criteria apply. The reason for removal from protocol therapy, and the date the participant was removed, must be documented in the case report form (CRF). Alternative care options will be discussed with the participant.

An ODQ Treatment Ended/Off Study Form will be filled out when a participant is removed from protocol therapy. This form can be found on the DF/HCC website at <http://www.dfhcc.harvard.edu/research/clinical-research-support/document-library-forms-sops-etc/>.

In the event of unusual or life-threatening complications, treating investigators must immediately notify the Overall PI, [name] at [contact] or [name].

## **5.8 Duration of Follow Up**

End of treatment assessment for all subjects will be collected within 28 days of last dose. All AEs must be followed for 28 days after the subjects last dose, or until resolution, whichever comes first. All SAEs must be followed to resolution or, if resolution is unlikely, to stabilization.

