## **10. STUDY CALENDAR**

Scans and x-rays must be done  $\leq$ 4 weeks prior to the start of therapy. Screening laboratory tests and ECG will be performed within 15 days prior to the start of therapy. In the event that the participant’s condition is deteriorating, laboratory evaluations should be repeated within 48 hours prior to initiation of the next cycle of therapy. Laboratory testing must be repeated if done more than 7 days prior to day 1.

Assessments must be performed prior to administration of any study agent. Study assessments and agents should be administered within  $\pm$  3 days of the protocol-specified date, unless otherwise noted. Dosing delays beyond noted windows for non-clinical reasons (e.g. weather, holidays) are permitted with approval of the overall PI.

	Pre-study	Cycle 1			Cycle 2 and beyond			Off Study H
		Wk 1	Wk 2	Wk 3	Wk 4	Wk 5	Wk 6	
Eribulin A		X	X		X	X		
Informed consent	X							
Pathology Review B	X							
Demographics	X							
Medical Hx	X							
Concurrent Meds	X	X	X		X	X		
Physical Exam	X	X	X		X	X		X
Vital Signs including weight	X	X	X		X	X		X
Height	X							
ECOG PS	X	X			X			X
Laboratory testing C	X	X	X		X	X		X
ECG	X I				X I			
Adverse Event Evaluation		X	X	X	X	X	X	X
Tumor Measurements D	X	Every 6 weeks for the first 7 cycles (before C3, C5, C7) and then every 9 weeks onward (before C10, C13, etc)						
Urine or serum B-HCG E	X							
Required Biopsy F	X						X	
Blood sample for cfDNA G		X			X			
A- Eribulin will be administered of 1.4 mg/m2 as an IV infusion over 2-5 minutes on Days 1 and 8 of every 21-day cycle B- Pathology review any time prior to the study C- CBC/diff, chemistries (sodium, potassium, chloride, bicarbonate, BUN, creatinine, glucose, calcium, phosphorus, magnesium, total bilirubin, alkaline phosphatase, AST, ALT, total protein, albumin); urinalysis only required on prescreening testing and PT/PTT only required on prescreening testing and before Biopsy 2. Screening laboratory tests will be performed within 15 days prior to Day 1 of treatment D- The modality (e.g. CT, MRI) should be consistent through the protocol. The window is +/- 1 week for the first 3 sets of scans/imaging then +/- 2 weeks thereafter; baseline tumor measurements should be performed within 28 days prior to Day 1 of treatment								

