- E- Urine or serum beta-HCG Must be repeated if not performed within 72 hours of cycle 1 day 1
- F- Biopsy 1 will occur after registration and prior to C1D1. Biopsy 2 will occur prior to the first imaging and C3D1. Platelet count and PT/PTT required pre biopsy 2 or per institutional standards. When possible the biopsy should be multiple cores or excisional. If the biopsy is considered unsafe the requirement may be waived after discussion with the overall PI.
- G- cfDNA will be collected after registration (prior to C1D1) and every D1 thereafter
- H- See section 5.8 for AE and SAE follow-up.
- I- ECG monitoring only required for screening, C2D1 and C3D1 unless the criteria for continued monitoring are met as per section 6.3. ECG does not need to be repeated on C1D1 if obtained within 15 days of C1D1, unless clinically indicated.

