#### For Participants with Measurable Disease (*i.e.*, Target Disease)

Target Lesions	Non-Target Lesions	New Lesions	Overall Response	Best Overall Response when Confirmation is Required*
CR	CR	No	CR	$\geq 4$ wks Confirmation**
CR	Non-CR/Non-PD	No	PR	$\geq 4$ wks Confirmation**
CR	Not evaluated	No	PR	
PR	Non-CR/Non-PD/not evaluated	No	PR	
SD	Non-CR/Non-PD/not evaluated	No	SD	Documented at least once $\geq 4$ wks from baseline**
PD	Any	Yes or No	PD	no prior SD, PR or CR
Any	PD***	Yes or No	PD	
Any	Any	Yes	PD	

\* See RECIST 1.1 manuscript for further details on what is evidence of a new lesion.  
 \*\* Only for non-randomized trials with response as primary endpoint.  
 \*\*\* In exceptional circumstances, unequivocal progression in non-target lesions may be accepted as disease progression.

Note: Participants with a global deterioration of health status requiring discontinuation of treatment without objective evidence of disease progression at that time should be reported as “*symptomatic deterioration*.” Every effort should be made to document the objective progression even after discontinuation of treatment.

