#### 11.1.5 Progression-Free Survival

Overall Survival: Overall Survival (OS) is defined as the time from randomization (or registration) to death due to any cause, or censored at date last known alive.

Progression-Free Survival: Progression-Free Survival (PFS) is defined as the time from randomization (or registration) to the earlier of progression or death due to any cause. Participants alive without disease progression are censored at date of last disease evaluation.

Time to Progression: Time to Progression (TTP) is defined as the time from randomization (or registration) to progression, or censored at date of last disease evaluation for those without progression reported.

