## 14. PUBLICATION PLAN

The results should be made public within 24 months of reaching the end of the study. The end of the study is the time point at which the last data items are to be reported, or after the outcome data are sufficiently mature for analysis, as defined in the section on Sample Size, Accrual Rate and Study Duration. If a report is planned to be published in a peer-reviewed journal, then that initial release may be an abstract that meets the requirements of the International Committee of Medical Journal Editors. A full report of the outcomes should be made public no later than three (3) years after the end of the study.

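### No tumour assessment or survival contact is scheduled for patients who stop eribulin without documented progression, which can bias PFS upward and leave some 24-week disease control status unknown

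*Combined protocol and SAP*

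**What the plan says.** **Follow-up.** Section 5.8, which sets the duration of follow-up, says "End of treatment assessment for all subjects will be collected within 28 days of last dose". The content of that assessment is not given and no scan is named. The rest of the section concerns safety: "All AEs must be followed for 28 days after the subjects last dose, or until resolution, whichever comes first", with serious events followed to resolution or stabilization. In the study calendar, the footnote to the Off Study column reads "See section 5.8 for AE and SAE follow-up".

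**Scans.** The calendar schedules tumour measurements "Every 6 weeks for the first 7 cycles (before C3, C5, C7) and then every 9 weeks onward (before C10, C13, etc". Sections 1.1 and 11.1 give the same cycle-based schedule. Section 13.4 instead has 6-week spacing for the first 8 cycles.

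**Leaving treatment and leaving the study.** Section 5.7 lists five reasons, besides progression, to stop protocol therapy: intercurrent illness, unacceptable toxicity, non-compliance, the participant's decision, and "General or specific changes in the participant's condition render the participant unacceptable for further treatment in the judgment of the treating investigator". Section 5.9 removes participants from the study only for loss to follow-up, withdrawal of consent for data submission, or death.

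**After discontinuation.** The note on symptomatic deterioration under the response table in Section 11.1.3.4 says "Every effort should be made to document the objective progression even after discontinuation of treatment". It gives no schedule.

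**Endpoints.** For PFS, Section 11.1.5 counts progression or death from any cause and adds "Participants alive without disease progression are censored at date of last disease evaluation". Section 1.3 defines disease control as the response rate plus stable disease at 24 weeks. Section 13.5 analyses disease control at 24 weeks with an exact binomial interval. Neither section says how to count a patient whose 24-week status is unknown.

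**Maturity.** Section 14 ties the end of the study to mature outcome data, "as defined in the section on Sample Size, Accrual Rate and Study Duration". Section 13.2 gives only the 16 patients and about 32 months of enrolment.

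**The concern.** A patient who has stopped eribulin has no further cycles, so a schedule written in cycles gives no dates for the next scan. Section 5.8, the natural place for such dates, gives none. The patient stays on study under Section 5.9, but the plan does not say what efficacy data to collect or until when.

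For PFS, the risk is informative censoring. Section 2.1 describes angiosarcoma as very aggressive, and patients who stop because of illness or a change in condition are plausibly closer to progression or death than those who continue. If their progression is not recorded, they are censored at the last scan that showed no progression, and the Kaplan-Meier curve treats them as if their later risk were average. A patient who stops before the first scan at week 6 is in effect censored at time zero unless an event is captured.

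For disease control, a patient who stops with stable disease before week 24 can be counted as controlled, counted as not controlled, or dropped. With 16 patients the choice is visible in the result, and it is left open until the data are known.

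**Working it through.** **1. The plan's own figure.** The documents give no dropout rate and no precision figure for PFS or disease control, so the only design figure available to check is the primary rule in Section 13.1. With X binomial (n = 16), P(X ≥ 4) is 0.866 at a 35% response rate (stated power 87%) and 0.068 at 10% (stated ceiling 10%). It reproduces. It is little affected by this point, because Section 13.6.2 keeps every treated patient in the response analysis.

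**2. Scan weeks.** Week = 3 × (cycle − 1). Scans before C3, C5, C7, C10 and C13 fall at weeks 6, 12, 18, 27 and 36. The calendar's window is ±2 weeks after the first three sets of scans, so the C10 scan falls in weeks 25 to 29. The calendar has no week-24 scan even for patients still on treatment. The 8-cycle wording in Section 13.4 would put one before C9, at 3 × 8 = week 24.

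**3. PFS, upper bound.** Inputs:
- median PFS 2.1 months, from the other-sarcoma stratum of the earlier phase 2 study in Section 2.2.3; 2.1 × 30.44 / 7 = 9.13 weeks;
- exponential times (assumption);
- a fraction f of patients leaves just before progression, is censored at the previous scan, and has no later progression or death recorded (assumption); f = 0, 2/16, 4/16, 6/16.

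Let q be the true probability of staying progression-free between two scans: q₆ = exp(−ln 2 × 6 / 9.13) = 0.634 and q₉ = exp(−ln 2 × 9 / 9.13) = 0.505. A leaver who progresses in an interval was censored at its start, so the Kaplan-Meier factor at the next scan is

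g = q / [q + (1 − f)(1 − q)].

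PFS at week 12 is g₆²; at week 27 it is g₆³ × g₉.

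| Leavers of 16 | g₆ | g₉ | Week 12 | Week 27 |
|---|---|---|---|---|
| 0 | 0.634 | 0.505 | 40% | 13% |
| 2 | 0.664 | 0.538 | 44% | 16% |
| 4 | 0.698 | 0.576 | 49% | 20% |
| 6 | 0.735 | 0.620 | 54% | 25% |

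The estimated median is the week-12 scan for 0, 2 or 4 leavers. It moves to the week-18 scan only with 6, where the estimate at week 12 is still above 50%.

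**4. Disease control.** Each unknown patient is worth 1/16 = 6.25 points. As an example, take 6 of 16 known to be controlled and 3 unknown:
- counted as not controlled: 6/16 = 37.5% (exact 95% interval 15% to 65%);
- dropped: 6/13 = 46.2% (19% to 75%);
- counted as controlled: 9/16 = 56.3% (30% to 80%).

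The range is 3 × 6.25 = 18.8 points. At assumed rates of 10% and 20% leaving before progression, 1.6 and 3.2 of 16 patients would be expected to leave.

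**The case against.** A reader might infer that assessments stop when eribulin stops and that follow-up ends 28 days after the last dose. The documents do not say so. Section 5.9 keeps these patients on study, Section 5.8 follows serious events beyond 28 days, and Section 11.1 asks for re-evaluation at 6- and then 9-week intervals without limiting it to patients on treatment, although it names cycles. The end-of-treatment assessment might include a scan. The supportable statement is that nothing is scheduled and the sections need reconciling.

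A reader might also infer that later deaths cannot be captured. Section 5.9 lists death as an off-study reason and requires the reason and date on the case report form, and the overall-survival definition presupposes a date last known alive. Deaths are PFS events, so not every leaver is censored. What is missing is a schedule of contacts to find them.

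The PFS figures describe patients who stop close to progression, and the deteriorating patients among them are the group for whom Section 11.1.3.4 asks for every effort. The calculation assumes that this effort always fails. It is therefore a ceiling for a given number of leavers, and that number is assumed. At 2 of 16 the shift is 4 points at week 12 and 3 at week 27. The standard error of a 40% proportion in 16 patients is √(0.4 × 0.6 / 16) = 12 points, a 95% half-width of about 24, so even the 14-point extreme lies within sampling error. That limits the practical consequence, but the bias has a predictable direction and the confidence interval does not reflect it.

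Nor is every leaver unknown for disease control. Under Section 1.3, a patient who responded before leaving may count as controlled. Section 13.5 can be read as requiring status at week 24, but only patients last seen with stable disease are unknown on both readings.

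Finally, the absence of a scan mark in the Off Study column is weak evidence, because the table may have merged cells. The point rests on Sections 5.8, 11.1 and 11.1.5 and the calendar footnote.

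**Conclusion.** The point holds for the two secondary efficacy endpoints. The plan schedules no tumour assessment and no survival contact for patients who stop eribulin without documented progression, and its only instruction for that period is an effort-based note without dates. Combined with the censoring rule, this can bias PFS upward. It also leaves 24-week control undefined for patients last seen with stable disease, at 6.25 points each.

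The upper bound for PFS is a rise of 4 to 14 points at week 12 (40% to between 44% and 54%) and 3 to 12 points at week 27 (13% to between 16% and 25%). It assumes exponential times, a 2.1-month median, 2 to 6 of 16 patients leaving just before progression, and none of their progressions or deaths captured. The true effect will be smaller to the extent that sites scan and record deaths on their own initiative.

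The decision rule of at least 4 responses in 16 is little affected, and PFS and disease control carry no test or threshold. This is a modest point, worth correcting because the correction is cheap.

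**What to change.** **Sections 5.8, 5.9, 11.1 and the calendar.** Reconcile them with a statement that, for patients who stop eribulin without progression:
- routine-care scans are recorded on the existing schedule, expressed in calendar weeks, until progression, death or withdrawal of consent;
- the date of any new anticancer therapy is recorded, and its handling in PFS is stated;
- vital status is recorded by chart review or telephone to a stated data cut-off, which would also supply the maturity definition that Section 14 expects from Section 13.2.

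**Section 13.5, disease control.** First reconcile the scan schedule with the 8-cycle wording in Section 13.4. Then define 24-week control by the first scheduled scan at or after week 24, with its window; under the calendar this is the C10 scan, weeks 25 to 29. Without that window, patients still on treatment and controlled could be failed merely because the calendar has no week-24 scan. Keep all treated patients in the denominator, and count those without such an assessment showing CR, PR or SD as not controlled.

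**Section 13.5, PFS.** Add a sensitivity analysis that counts stopping for clinical deterioration as an event.

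**Cost.** A short amendment, a few extra data items for a few patients, and a slightly less favourable disease control rate. The sensitivity analysis uses the stopping reason that Section 5.7 already requires on the case report form.

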## **5.9 Criteria for Taking a Participant Off Study**

Participants will be removed from study when any of the following criteria apply:

- Lost to follow-up
- Withdrawal of consent for data submission
- Death

The reason for taking a participant off study, and the date the participant was removed, must be documented in the case report form (CRF).

For Decentralized Subject Registrations, the research team updates the relevant Off Treatment/Off Study information in OnCore.

